15.2 Objectives and Outcome Measures

These are detailed in full in [Section 3](#).

15.3 Analyses of Outcome Measures

15.3.1 Primary Outcome (Part I)

The final model determined MTD, which is the dose level with DLT probability estimated to be closest to the acceptable percentage (target DLT rate) of subjects experiencing a DLT, will be reported with its associated probability of DLT and 90% probability interval. All tolerable doses to be considered will be the MTD and doses below it. The recommended dose for Parts II and III will be selected based on the assessment of changes in immune function, PK and PD data.

15.3.2 Primary Outcome (Part II)

ORR, CBR and irORR will be reported as the proportion of subjects of all evaluable subjects within each tumour type cohort and dose. The 90% confidence intervals for ORR, CBR and irORR will be calculated. Simon's Two-Stage design will be used to evaluate efficacy and decide whether the cohort can be further expanded or not for Part III.

15.3.3 Primary Outcome (Part III)

ORR, CBR and irORR will be reported as the proportion of subjects of all evaluable subjects within each tumour type cohort. The 90% confidence intervals for ORR, CBR and irORR will be calculated. Duration of response is measured from the time of initial response until documented tumour progression, death or dropout.

15.3.4 Secondary and Exploratory Outcomes

15.3.4.1 Monocytes CLEVER-1 positivity

The proportion of CLEVER-1-positive monocytes in the blood total monocyte population will be measured by flow cytometry from blood samples collected over time during the first four cycles. Results will be reported with descriptive statistics. Also explorative statistical analyses will be conducted for the flow cytometry data, if feasible.

15.3.4.2 sCLEVER-1

sCLEVER-1 and its occupancy by FP-1305 in the blood will be measured by immunoassay over time during the first cycles. Results will be reported with descriptive statistics. Also explorative statistical analyses will be conducted for the data, if feasible.

15.3.4.3 Pharmacokinetic Parameters

The serum concentration of FP-1305 will be determined by a validated method according to the assessment schedules. The concentrations will be summarized by visit and the sampling time using descriptive statistics by the dose level. Only subjects who have received the whole dose at each infusion will be used for the repeated PK analysis. The mean concentration will be plotted against the scheduled sampling times. A tabulated summary with descriptive statistics will be given.

15.3.4.4 Immunogenicity

Anti-human FP-1305 antibodies will be assessed analysed by a validated method. Immunogenicity results will be summarized by listing of all available immunogenicity data. The frequency of positivity will be given by dose and cohort. The correlation of AEs and immunogenicity may be examined.

15.3.4.5 Safety

Safety and tolerability will be reported through the assessment of observed adverse events in the subjects. The number of cases and the number of subjects that these cases occurred in will be reported for each event. Drug-related events are reported in a separate table. In addition, both DLTs and drug-related serious adverse events are reported separately in a tabular format, and their seriousness will be assessed based on the NCI-CTCAE classification. AEs are also to be evaluated stratified by dose level and by disease group.

15.4 Analysis of Efficacy Parameters

The proportion of CLEVER-1-positive monocytes in the blood total monocyte population will be measured by flow cytometry from blood samples collected over time during the first four cycles. The results will be reported with descriptive statistics.

Tumour samples collected before and during the treatment will be stained for CLEVER-1. The proportion of CLEVER-1 positive TAMs will be analysed by immunohistochemistry. Macrophage mannose receptor and/or other markers may be used to determine the total content of TAMs. The proportion of CLEVER-1 positive cells prior to and during the treatment will be reported using descriptive statistics. The correlation between circulating CLEVER-1-positive monocytes and CLEVER-1 expression in tumour macrophages will be calculated before and during the treatment. The correlation of the parameters obtained during Cycle 1 with ORR, CRB and irORR rates will also be calculated for subjects included into the ORR/CBR/irORR analysis. The results will be summarized using descriptive statistics. If feasible, exploratory statistical analyses will also be used to describe the associations.

The proportion of lymphocyte subsets (CD4, CD8, their ratio, NK-cells, B-cells and regulatory T-cells), and macrophage HLA expression and myeloid derived suppressor cell populations in circulation will be analysed at given time points with flow cytometry and plotted against the scheduled sampling time. The level of circulating cytokines and chemokines (these may include but are not limited to the following IFN α , IFN γ , IL-1 α , IL-1 β , IL-1RA, IL-2, IL-4, IL-5, IL-6, IL-7, IL-8/CXCL8, IL-9, IL-10, IL-12p70, IL-13, IL-15, IL-17A, IL-18, IL-21, IL-22, IL-23, IL-27, IL-31, TNF alpha, TNF beta, GM-CSF, Eotaxin/CCL11, GRO alpha/CXCL1, IP-10/CXCL10, MCP-1/CCL2, MIP-1 α /CCL3, MIP-1 β /CCL4, RANTES/CCL5, SDF-1 α /CXCL12) will be analysed by multiplex assays pre- and post-treatment. Aggregated data (mean and median) from each dose level will be presented using descriptive statistics by tumour type cohort.

ORR, CBR and irORR will be reported as the proportion of subjects of all evaluable subjects within each tumour type cohort. The 95% confidence intervals for the ORR, CBR and irORR will be calculated.

The change in LDH, LDL and OxLDL, CRP, CA-125 (OC subjects), CA19-9 (PDAC, gallbladder cancer, cholangiocarcinoma, gastric adenocarcinoma subjects), CEA (CRC, ER+ BC, gastric adenocarcinoma subjects), CA-15-3 (ER+ BC subjects) and AFP (HCC subjects) levels in the subjects pre- and post-treatment will be reported with descriptive statistics.

The correlation of the response according to RECIST 1.1 defined responses (CR/PR/SD/PD) with the immune cell profile, the level of circulating cytokines and chemokines, CLEVER-1 on circulating monocytes, and possible genetic analyses during the first four cycles of treatment will be reported using descriptive statistics. If feasible, exploratory statistical analyses will also be used to describe the associations.

The receptor occupancy of FP-1305 on the circulating monocytes during Part I and in some subjects during Part II will be analysed using flow cytometry and will be plotted against scheduled sampling times. Aggregated data (mean and median) from each dose level will be presented by tumour type cohort. The results will be summarized using descriptive statistics.

Free sCLEVER-1 in the circulation will be measured with immunoassay.

Overall survival data, including but not limited to the six-month, one-year and two-year survival rates will be reported for each cohort, and will be analysed using the Kaplan-Meier method and cox-modelling where appropriate.

Progression free survival including but not limited to the six-month, one-year and two-year survival rates will be reported for each tumour type cohort and will be analysed using the Kaplan-Meier method and cox-modelling where appropriate.

15.5 Planned Interim Analysis

There is no predefined interim analysis. Interim analyses on safety and efficacy or on PK, immunogenicity, and selected biomarkers may be provided on ongoing basis prior to completion of the trial in order to expedite conclusions and to support trial presentations or publications.

15.6 Planned Main Analyses

Part I

The main analysis for determining the recommended dose to be expanded upon will take place once all subjects in part I have been recruited to trial and have been followed-up for the 9-week DLT assessment period.

Part II

Each cohort will be analysed when ten evaluable subjects have been accrued and treated with the selected dose. Subjects from Part I can be included into the cohort of ten subjects if they have been treated with the selected dose.

Part III

Each cohort that is continued after the analysis of Part II will be analysed when 29 evaluable subjects have been accrued and treated with optimal dose or until the required 4 responders are reached. The cohort can continue accruing subjects if the stopping rule is not met. The final analysis of each cohort is when the particular cohort has been considered complete.

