15.7 Power Calculations

The operating characteristics of the TITE-CRM will be assessed to assure the design is well calibrated for determining the MTD. Fine-tuning of the model to tailor to the trial's requirements will be aided with the use of the Dose-Transition Pathways, which maps out in advance how the model will recommend doses for all permutations of DLT outcomes for the initial subjects (Yap et al, 2017). Details of the TITE-CRM is presented in the corresponding statistical analysis plan. Part II and Part III are based on adaptive Simon's Two-Stage design, with the following assumptions Type I error rate (α ; one-sided) 0.05, power 0.80, response probability in the palliative treatment 5% (alternative option for these subjects) and response in the trial treatment 20%, 10 subjects in each cohort with at least one subject that demonstrates clinical benefit (CBR by RECIST 1.1 criteria) in the Part II is needed to conclude that the cohort may be expanded. Additionally, data from Part II will be used to determine CLEVER-1 positivity in each of the cohorts. If it is possible that cohorts can be divided in

the CLEVER-1 positive and CLEVER-1 negative groups, both subgroups will be expanded in Part III so that 10 subjects in each group are recruited. In case there are 10/10 non-responders in either of the subgroups, then the recruitment will continue only in the other subgroup with responders. The recruitment can continue within that subgroup until the planned maximum of 29 subjects (or until the required 4 subjects that demonstrate clinical benefit are reached). If the subgroups cannot be defined, the Part III continues with the original cohorts having 1 responder in the cohort. In case there are clearly more negative than positive subjects in some cohort, and also clear difference in the response, the DMC will evaluate the data and decide further cohort expansions.

If the desirable response is obtained in Part III of the trial the cohort(s) may be further expanded.

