- The proportion of lymphocyte subsets (CD4, CD8, their ratio, NK-cells, B-cells and regulatory T-cells), and plotted against the scheduled sampling time. The level of circulating cytokines and chemokines (including but not necessarily limited to IFN γ , IL-1 β , IL-2, IL-4, IL-6, IL-8/CXCL8, IL-10, IL-12p70, IL-13 and TNF alpha, IP-10/CXCL10, Eotaxin/CCL11, MCP-1/CCL2, MIP-1 α /CCL3, MIP-1 β /CCL4) will be analysed by multiplex assays prior to and during the treatment.
- LDH, LDL, oxLDL, and CRP, as well as the following tumour specific markers CA-125 (OC subjects), CA19-9 (PDAC, gallbladder cancer, cholangiocarcinoma, gastric adenocarcinoma subjects), CEA (CRC, ER+ BC, gastric adenocarcinoma subjects), AFP (HCC subjects), CA-15-3 (ER+ BC subjects) levels prior to and during the treatment will be measured from blood.

6 Sample size considerations

In Part I 30 subjects were enrolled, in Part II up to 10 subjects in each selected Part II cohort (cancer type, dose level and dosing scheme) will be enrolled; in addition, testing of higher doses (30-100 mg/kg) in cohorts with multiple cancer types will proceed in parallel with the treatment of other Part II cohorts. In Part III additional subjects will be enrolled based on the continuation rules set in this protocol. Subjects are enrolled into a specific part of the study and continue in that part until they discontinue (i.e. subjects do not proceed from one part to the next part). It is estimated that the total number of subjects in the whole trial is up to 700.

7 Statistical hypotheses

Expansion of each cohort to Part III of the trial is based on the predefined rule applying Simon's 2-stage design. Clinical benefit ratio (CBR) of 1/10 is needed in order to expand the cohort up to a total of 29 subjects per cohort.

8 Analysis datasets

Following analysis populations have been described in the protocol:

Safety population: Includes all subjects who have received any amount of FP-1305. This formulates the Full Analysis Set for Safety (FAS-S).

DLT evaluable population: Includes all subjects in Part I who have received at least one dose of FP-1305 and followed up for at least three weeks. Any subject that withdraws, discontinues from the trial or dies not related to treatment prior to the end of the 9-week DLT assessment period will be replaced.

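### A Part III cohort may be analysed at its fourth subject with clinical benefit, yet its benefit rate is reported as a plain proportion with a 90% CI, as if the sample size were fixed

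*Protocol*

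**What the plan says.** **Design.** Protocol 15.7 describes an adaptive Simon two-stage design with the error settings "one-sided) 0.05, power 0.80", a null rate of 5% and a target rate of 20%. The go rule is "10 subjects in each cohort with at least one subject that demonstrates clinical benefit". Section 7 of the Part II SAP says that a CBR of 1/10 "is needed in order to expand the cohort up to a total of 29 subjects per cohort", so the 29 includes the first 10.

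**When Part III is analysed.** Protocol 15.6: a continued cohort "will be analysed when 29 evaluable subjects have been accrued and treated with optimal dose or until the required 4 responders are reached". The parallel wording in 15.7, written for the CLEVER-1 subgroup branch, is "or until the required 4 subjects that demonstrate clinical benefit are reached". The counted event there is clinical benefit; 15.6 says responders.

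**What is reported.** Protocol 15.3.3 gives ORR, CBR and irORR as proportions of all evaluable subjects in each tumour-type cohort, and adds: "The 90% confidence intervals for ORR, CBR and irORR will be calculated". It names no interval method and makes no allowance for the stop or for the stage-1 selection. Section 15 foresees a separate SAP for each part; the SAPs available cover Parts I and II.

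**The concern.** When a cohort can close on a success, the number of subjects depends on the results. A run of early benefits closes the cohort while the observed rate is high; a slow start lets it run on to 29. A plain proportion treats both as fixed-size samples. The go rule adds a second selection, because a cohort reaches Part III only if at least one of its first ten subjects benefited.

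CBR is a primary outcome of Part III (protocol 3.7 and 3.10). At stake is the benefit rate quoted for each cohort that goes forward. The decision to call a cohort successful is not at stake.

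**Working it through.** **Inputs.** From 15.7: p0 = 0.05, p1 = 0.20, one-sided alpha 0.05, power 0.80, stage 1 of 10 with at least 1 benefit to go on, 4 required. From Part II SAP section 7: 29 in total.

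**1. The plan's own design.** A search for Simon's optimal design under these settings returns exactly 0/10 and 3/29, that is, stop at 0 of 10 and succeed with 4 or more of 29. Attained alpha is 0.0468 and power 0.801. Stopping once 4 is reached cannot change who reaches 4, so both figures are the same with the stop.

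**2. Chance of expansion.** P(expand) = 1 − (1 − p)^10, which is 0.893 at p = 0.20 and 0.401 at p = 0.05.

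**3. Mean plain CBR in an expanded cohort.** With all 29 enrolled it is [10p / P(expand) + 19p] / 29:
- p = 0.20: (2 / 0.8926 + 3.8) / 29 = 0.208
- p = 0.05: (0.5 / 0.4013 + 0.95) / 29 = 0.076

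With the stop, all paths were enumerated: ten subjects, then one at a time until the 4th benefit or n = 29. Each end point (x, n) contributes x/n, weighted by its probability.

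| True CBR | Stop at 4 | All 29 enrolled | Excess from go rule | Excess from stop |
|---|---|---|---|---|
| 5% | 8.1% | 7.6% | 2.6 | 0.5 |
| 10% | 13.8% | 11.9% | 1.9 | 1.9 |
| 20% | 24.6% | 20.8% | 0.8 | 3.8 |
| 30% | 33.8% | 30.3% | 0.3 | 3.5 |

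The last two columns are in percentage points: column 3 minus the truth, and column 2 minus column 3. At a true 20%, 88% of expanded cohorts reach 4 before subject 29.

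**4. Averaged over all cohorts.** Cohorts ended at 0/10 contribute zero, so the mean is the step 3 value times P(expand):
- p = 0.20: 0.2464 × 0.8926 = 0.220
- p = 0.05: 0.0806 × 0.4013 = 0.032, below the truth

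**5. A stopping-rule estimate.** The unbiased estimate (UMVUE) at (x, n) is the number of paths to that point that begin with a benefit, divided by all paths to it.
- 4/12: C(10,2) / C(11,3) = 45/165 = 27.3%, against a plain 33.3%
- 4/15: C(13,2) / [C(14,3) − C(4,3)] = 78/360 = 21.7%, against 26.7%
- 4/20: 17.3%, against 20.0%
- 1/29: 1/10 = 10.0%, against 3.4%

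Its mean over all cohorts is p. It is zero at 0/10, so its mean given expansion is p / P(expand): 0.20 / 0.8926 = 22.4% and 0.05 / 0.4013 = 12.5%.

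**6. Over-running.** Suppose extra subjects are already enrolled when the 4th benefit is read (the numbers are assumptions, capped at 29 in total). At a true 20% the excess is 4.6 points with none, 3.0 with four and 2.0 with eight.

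**7. Interval.** The documents name no method; an exact Clopper-Pearson 90% interval is assumed. In expanded cohorts its coverage is 0.894 at a true 5% and 0.93 to 0.97 for true rates from 10% to 50%. The lower limit lies above the truth in 10.6% of expanded cohorts at a true 5%, against 3.1% if all 29 are enrolled.

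**The case against.** Several points on the other side are sound.

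- **The stop is permissive.** Section 15.6 sets when a cohort is analysed and puts the final analysis at the point where the cohort is considered complete. Section 15.7 lets a successful cohort expand further. Benefit is read from imaging at Cycle 4 or later, so some over-running is likely. This stands: 24.6% is an upper figure, for an immediate stop under the cumulative reading.
- **The direction depends on the averaging and the reading.** Over all cohorts the plain rate is too low at a true 5%. If cohorts with 4 or more of 10 never enter Part III, the mean for the rest is 21.7% at a true 20% but 26.8% at a true 30%, which is downward. If Part III counts afresh, it is 24.2% at a true 20% and 5.2% at a true 5%. A reader might infer that every reported rate is too high, or that unexpanded cohorts go unreported. Neither follows: Part II reports each ten-subject cohort separately.
- **The unbiased estimate is not a clean replacement.** A reader might infer that it should become the primary estimate. Given expansion it averages 12.5% at a true 5%, further from the truth than the plain 8.1%, and it reports a failed 1/29 as 10.0%.
- **The interval conflict is slight.** A reader might infer that the CI contradicts the success rule. Under the assumed exact method the lower limit at exactly 4/29 is 4.85% against a null of 5%, and no section uses the interval for the decision.
- **A Part III SAP may add an adjustment.** It may. But 15.3.3 already fixes the plain proportion, and nothing available qualifies it.

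**Conclusion.** The concern holds for the point estimate. As written, the plan lets a cohort be analysed at its fourth subject with clinical benefit and reports a primary rate that ignores this. For an expanded cohort at the 20% design target the excess is up to 4.6 points, mainly from the stop. At the 5% null it is 3.1 points, mainly from the go rule. These figures assume an immediate stop, a cumulative 10 + 19, and that cohorts with 4 or more of 10 count as expanded. They do not cover the CLEVER-1 subgroup branch, where ten subjects per subgroup are recruited within Part III.

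Alpha 0.0468 and power 0.801 stand, and overall interval coverage is largely kept. ORR and irORR are affected only through their overlap with clinical benefit, since that is the event that triggers the stop.

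**What to change.** In protocol 15.3.3 and 15.6 and in the Part III SAP:

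1. State that the fourth subject with clinical benefit settles only the success decision, and that the primary CBR estimate uses the planned 29 evaluable subjects. Use clinical benefit as the counted event in both 15.6 and 15.7.
2. Where a cohort does end early, report beside the plain proportion an estimate and 90% CI computed for the two-stage, stop-at-4 rule. Label it as unbiased over all cohorts and not conditional on expansion. Do not make the UMVUE the sole primary estimate.
3. Name the interval method. Section 15.4 asks for 95% intervals on the same rates, so settle the level in the same edit.

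**Cost.** Item 1 means that cohorts reaching 4 early accrue on to 29. At a true 20% the mean size of an expanded cohort under an immediate stop is 18.3, so this adds about 29 − 18.3 = 10.7 subjects on average, all within the planned maximum. At a true 5% it adds about 29 − 28.2 = 0.8. Item 2 needs only wording and a short calculation, but the adjusted rate is less favourable in cohorts that stop soon after stage 1. Alpha and power do not change. The choice should be made before any Part III cohort is analysed.

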15.7 Power Calculations

The operating characteristics of the TITE-CRM will be assessed to assure the design is well calibrated for determining the MTD. Fine-tuning of the model to tailor to the trial's requirements will be aided with the use of the Dose-Transition Pathways, which maps out in advance how the model will recommend doses for all permutations of DLT outcomes for the initial subjects (Yap et al, 2017). Details of the TITE-CRM is presented in the corresponding statistical analysis plan. Part II and Part III are based on adaptive Simon's Two-Stage design, with the following assumptions Type I error rate (α ; one-sided) 0.05, power 0.80, response probability in the palliative treatment 5% (alternative option for these subjects) and response in the trial treatment 20%, 10 subjects in each cohort with at least one subject that demonstrates clinical benefit (CBR by RECIST 1.1 criteria) in the Part II is needed to conclude that the cohort may be expanded. Additionally, data from Part II will be used to determine CLEVER-1 positivity in each of the cohorts. If it is possible that cohorts can be divided in

the CLEVER-1 positive and CLEVER-1 negative groups, both subgroups will be expanded in Part III so that 10 subjects in each group are recruited. In case there are 10/10 non-responders in either of the subgroups, then the recruitment will continue only in the other subgroup with responders. The recruitment can continue within that subgroup until the planned maximum of 29 subjects (or until the required 4 subjects that demonstrate clinical benefit are reached). If the subgroups cannot be defined, the Part III continues with the original cohorts having 1 responder in the cohort. In case there are clearly more negative than positive subjects in some cohort, and also clear difference in the response, the DMC will evaluate the data and decide further cohort expansions.

If the desirable response is obtained in Part III of the trial the cohort(s) may be further expanded.

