2.5.1 Hepatobiliary Cancers

Hepatobiliary tumours comprise several major global cancers including hepatocellular (HCC) and biliary tract cancers (Kabbach et al. 2015). Biliary tract cancers are sub-classified into intrahepatic cholangiocarcinoma, originating from the biliary tree within the liver, and extrahepatic cholangiocarcinoma, outside the liver parenchyma; the latter is further subdivided into perihilar cholangiocarcinoma and distal cholangiocarcinoma, with a frequency of 10%–20% intrahepatic, 50% perihilar and 30%–40% extrahepatic cholangiocarcinoma (Valle et al. 2016).

Despite advances in surgical techniques and chemotherapeutic agents, the overall survival in these patients remains extremely poor. Statistics from Cancer Research UK demonstrate that since the 1970s liver cancer rates have more than tripled (236% increase) in Great Britain and a study from two major UK centres demonstrate an overall 5-year survival of less than 20% for these patients (Than et al. 2017).

The Barcelona Clinic Liver Cancer (BCLC) staging system is widely used and encompasses all HCC patients. The system identifies those patients with early HCC who may benefit from curative therapies (stage 0 and A), those at intermediate (stage B) or advanced stage (stage C) who may benefit from palliative treatments and those with a very poor life expectancy (stage D). Median survival without therapy is >36 months for stage 0 and A, 16 months for stage B, 4–8 months for stage C and <4 months for stage D. Over 50% of patients with moderately or poorly differentiated HCC are CLEVER-1 positive and this positivity correlates with low CD8/FoxP3 ratio (see [Figure 2](#) in [Section 2.3](#))

Sorafenib is the standard systemic therapy for patients with advanced HCC and well-preserved liver function (BCLC stage C) and those with intermediate-stage HCC who progress following transarterial chemoembolization. In case of disease progression or intolerance to sorafenib, best supportive care or inclusion into clinical trials for new therapeutic agents are the only options for patients. Systemic chemotherapy, tamoxifen, immunotherapy, anti-androgen or somatostatin analogues are not recommended for the clinical management of HCC patients (Verslype et al. 2012). Thus, there is a high unmet medical need for HCC patients.

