Part II of the trial will involve expansion groups of subjects by tumour type. The following tumour types will be selected for cohort expansion after the data of the first part of the trial has been reviewed: advanced hepatocellular carcinoma, cholangiocarcinoma and gallbladder cancer, pancreatic ductal adenocarcinoma, ovarian cancer, colorectal adenocarcinoma, cutaneous melanoma, uveal melanoma, gastric adenocarcinoma (including GE junction), ER+ breast cancer and anaplastic thyroid cancer. Each cohort will contain 10 subjects in Part II (10 at each dose level with random allocation within the same dosing schema Q3W, Q2W or Q1W. In addition, new dose level(s) 30 mg/kg and possibly also 45 and 100 mg/kg that include more than one tumour type will be tested for tolerability and safety. The data from both Part I and Part II will be used to define CLEVER-1 positivity in each tumour type. In Part III, subjects will be enrolled in tumour types that have demonstrated preliminary anti-tumour activity based on the CBR. Up to a total sample size of 700 subjects in all parts will be enrolled in approximately 20-30 sites in 5-8 countries. Subjects in Part III are stratified by disease type as in Part II and may be stratified by CLEVER-1 positivity. In Part II and Part III, cohorts for a particular tumour type may be opened sequentially or not opened at all i.e., if there is a strong signal for efficacy in cutaneous melanoma, that cohort may be opened first. Each cohort of subjects with a certain tumour type will be analysed for efficacy after 10 subjects have been treated with the dose(s) selected for Part II. The decision of continuing the cohort for Part III will be based on the results obtained from this analysis supported by the statistical rule to continue the cohort. Cohorts with best efficacy signal at any dose level may be advanced to Part III. However, it may not be meaningful to advance all Part II cohorts at any dose level with a minimal and clinically not meaningful signal of efficacy into Part III.

Figure 1A displays the trial pathway including dose escalation and expansion phases. **Figure 1B** displays how the initial design of the TITE-CRM will work in the absence of any DLT in Part I. Once a DLT is observed, subsequent dose decisions will be made with the usage of the TITE-CRM. This will take into account all accumulated DLT information—both partial (<9 weeks) and complete (9 weeks).

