- To assess the overall survival in trial subjects who receive at least 1 dose of FP-1305
- To measure cytokine and chemokine concentration in peripheral blood
- To measure the immune cell profile in circulation
- To assess if treatment elicits a change in LDH, LDL and oxLDL, CRP, CA-125 (OC subjects), CA19-9 (PDAC, gallbladder cancer, cholangiocarcinoma, gastric adenocarcinoma subjects), AFP (HCC subjects), CEA (CRC, ER+ BC, gastric adenocarcinoma subjects), CA-15-3 (ER+ BC subjects) levels or other relevant markers pre- and post-treatment

4 Design and type of the study

This is a prospective, three-part (see [Figure 1](#)) open label, Phase I/II dose-finding and separate cohorts expansion trial to determine the safety, tolerability and preliminary efficacy of repeated doses of CLEVER-1 antibody FP-1305 administered in three-weeks intervals (Q3W) in subjects with cutaneous melanoma, pancreatic ductal adenocarcinoma, ovarian cancer, colorectal adenocarcinoma, hepatocellular carcinoma, gallbladder cancer or cholangiocarcinoma, uveal melanoma, gastric (including GE junction) adenocarcinoma, ER+ breast cancer and anaplastic thyroid cancer.

In Part I 30 subjects were enrolled as planned. Part II consists of 10 enrolled subjects per cancer type (10 disease cohorts) at each selected Part II dose (1 mg/kg for all cohorts and 0.3 mg/kg, 1.0 mg/kg and 3.0 mg/kg for colorectal adenocarcinoma cohort) and dosing scheme (Q3W for all cancer types, Q2W and Q1W for selected cancer types). In addition to these, the study recruited cohorts for Q3W dosing of 3.0 mg and 10.0 mg for Cutaneous melanoma and Gastric adenocarcinoma, and also a cohort testing a higher dose (30.0 mg/kg) for any cancer cohort. Part III additional subjects will be enrolled based on the continuation rules set in the protocol (cohorts with at least 1/10 Clinical Benefit Rate will be expanded to total of 29 evaluable subjects). Thus, it is estimated that the total number of subjects in the whole trial can be up to 700 enrolled subjects.

In the study protocol, the study drug is set to be administered Q3W intervals. Based on the analysis of the PK, receptor occupancy and pharmacodynamic during the Q3W administration, it was deemed necessary to study more frequent dosing. With a country specific addendum, Q2W and Q1W dosing intervals are implemented into Part II. These are evaluated as separate Part II expansion cohorts.

[figure not shown]

Figure 1. Study design

5 Study variables

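### The 0.80 power in section 15.7 holds for a cohort not divided by CLEVER-1; the split path has no stated power, and the Part III analysis set and interval level conflict between sections

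*Protocol*

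**What the plan says.** Protocol 15.7 bases Parts II and III on a Simon two-stage design with one-sided alpha 0.05, "power 0.80, response probability in the palliative treatment 5% (alternative option for these subjects) and response in the trial treatment 20" per cent. A cohort may be expanded if at least 1 of 10 Part II subjects shows clinical benefit. If the cohort can then be divided by CLEVER-1, "both subgroups will be expanded in Part III so that 10 subjects in each group are recruited". A subgroup with no responder in 10 stops. For the other, the rule is "The recruitment can continue within that subgroup until the planned maximum of 29 subjects (or until the required 4 subjects that demonstrate clinical benefit".

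The split is conditional. Section 4 says "Subjects in Part III are stratified by disease type as in Part II and may be stratified by CLEVER-1 positivity". A further provision in 15.7, "In case there are clearly more negative than positive subjects in some cohort, and also clear difference in the response, the DMC will evaluate", hands such cases to the committee.

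The Part II SAP repeats only the cohort rule. Its section 4 has "cohorts with at least 1/10 Clinical Benefit Rate will be expanded to total of 29 evaluable subjects", and its section 7 has "Clinical benefit ratio (CBR) of 1/10 is needed in order to expand the cohort up to a total of 29 subjects per cohort".

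On the Part III primary endpoint:
- Objective 3.7 concerns CLEVER-1-positive subjects; 15.3.3 takes proportions of all evaluable subjects in the tumour-type cohort.
- Intervals for ORR, CBR and irORR are 90% in 15.3.2, 15.3.3 and Part II SAP 12.1, but 95% in 15.4, which is not limited to one part.
- 15.6 and 15.7 let accrual end at the fourth responder. CBR is nevertheless a plain proportion.

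**The concern.** Section 15.7 states one power figure and then describes two routes. On the split route a positive subgroup succeeds only if an unselected Part II cohort passes 1/10, the subgroup passes its own 1/10, and it reaches 4 of 29. No power is given for that sequence. The text does not say outright which group the 20% describes, or whether Part II subjects count toward the subgroup's 10 and 29. Because objective 3.7 names CLEVER-1 positives, a reader could take 80% as the overall chance of detecting a 20% rate in them.

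The conflicts over analysis set and interval level leave the reporting of the Part III primary endpoint open. Stopping at a success count also raises the expected observed rate, and no method is given for that.

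**Working it through.** **Inputs.** Null 5%, alternative 20%, at least 1/10 and then at least 4/29 are from 15.7. CLEVER-1 prevalence and the negatives' rate are assumptions. The only prevalence in the documents is background, for one tumour type: "Over 50% of patients with moderately or poorly differentiated HCC are CLEVER-1 positive". I used prevalence 30, 50 and 75%, with negatives at 5, 10 and 20%. All results are exact binomial.

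**1. The plan's own figure.** S(p) = sum over x = 1..10 of P(Bin(10,p) = x) × P(Bin(19,p) ≥ 4 − x).
- At 20%: 0.2684×0.7631 + 0.3020×0.9171 + 0.2013×0.9856 + 0.1209×1 = 0.801.
- At 5%: 0.3151×0.0665 + 0.0746×0.2453 + 0.0105×0.6226 + 0.0010 = 0.047.

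Both stated values are reproduced.

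**2. Split path with 20% in positives.** Let m = prevalence × 0.20 + (1 − prevalence) × negatives' rate. The Part II cohort passes with probability 1 − (1 − m)^10.
- 29 new positives needed: power = [1 − (1 − m)^10] × S(0.20).
- Part II positives counted: power = S(0.20) minus the probability that the positives would have succeeded although all 10 Part II subjects failed. The latter is summed over the number of positives among the 10.

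Worked case, prevalence 50%, negatives 5%: m = 0.125 and the Part II pass is 1 − 0.875^10 = 0.737. New: 0.737 × 0.801 = 0.590. Counted: 0.801 − 0.151 = 0.650. The counted figure given a Part II pass is 0.650/0.737 = 0.882.

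| Negatives' rate | Counted, prevalence 30/50/75% | New, 30/50/75% | Not split, 30/50/75% |
|---|---|---|---|
| 5% | 55/65/74% | 51/59/67% | 26/44/65% |
| 10% | 63/69/75% | 60/64/68% | 47/59/71% |
| 20% | 73/74/77% | 72/72/72% | 80/80/80% |

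Over prevalence 1-99% and negatives at 0, 5, 10 and 20%, the maximum is 0.7995 counted and 0.715 new. Given a Part II pass, power is 81.7-89.2% counted (table cells) and 80.1% new.

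**3. Split path with 20% in the whole cohort.** Positives' rate = (0.20 − (1 − prevalence) × negatives' rate)/prevalence.
- Negatives 5%: positives at 55/35/25%; power 89/89/86% counted, 89/88/81% new.
- Negatives 10%: power 89/87/84% counted, 89/86/79% new.
- Negatives 20%: positives are also at 20%, so the last row of the table applies.

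**4. Type I error, positives at 5%.** 1.9-4.4% at these prevalences. It cannot exceed S(0.05) = 4.7%, because the Part II condition can only lower it.

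**5. Stopping at the fourth benefit, true rate 20%.** The mean observed CBR among continued groups is 24.6% if accrual stops at once, 22.7% with 5 more enrolled, 21.7% with 10 more and 20.8% with all 29. The 5 and 10 are assumptions.

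**The case against.** A reader might infer that 0.80 is an arithmetic error, that alpha is inflated, or that the split harms the trial. The documents support none of these. The 0.80 is right for the design it is stated with. Type I error per subgroup stays at or below 0.05. When negatives respond less, splitting mostly does better than not splitting: always if Part II positives count, and with 29 new positives until prevalence reaches about 78% (negatives 5%) or 67% (negatives 10%).

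A reader might also infer that the trial is underpowered for CLEVER-1 positives. That needs the 20% to be theirs. In 15.7 the 5%, the 20%, alpha and power share a sentence with the 10 subjects per cohort, and CLEVER-1 enters only afterwards, so the cohort is the more natural reference. Only one of the 12 values in step 3 with negatives at 5% or 10% is then below 0.80 (79%). Once a cohort has passed Part II, a 20% rate in positives is detected with at least 80% power. If both subgroups are at 20%, the chance that at least one succeeds is 86-87%. The split is conditional, and the committee provision may remove the low-prevalence cases.

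All of this stands. It does not supply the missing figure or the counting rule. The SAP's total of 29 points to counting Part II subjects, but it speaks of cohorts, not subgroups. Section 15 promises a separate Part III SAP that is not among the documents. It could add detail, but the conflicts between 3.7 and 15.3.3 and between 15.3.3 and 15.4 lie within the protocol. On the stopping rule, continuing accrual is permitted and makes the bias small, so the plain proportion is defensible if all 29 are enrolled, less so if accrual ends at once.

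**Conclusion.** The point holds as a gap and two inconsistencies, not as an error in the stated power. Power 0.80 and alpha 0.05 belong to the undivided cohort at 20%. With the 20% assigned to positives, overall power from the start of Part II is below 0.80 at every prevalence under 100% (51-77% in the cases shown). With the 20% assigned to the whole cohort and negatives at 5% or 10%, it is 79-89%. These ranges rest on assumed prevalence and negative-group rates, and the distance between them is why the reference group should be named.

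The conflicts over analysis set and interval level rest on no assumption. For Part II the SAP already settles the interval at 90%; for Part III it is open. The upward bias in CBR is up to 4.6 points (24.6% against 20%) and depends on how soon accrual stops.

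**What to change.** 1. In 15.7, say that 0.80 refers to the undivided cohort at 20%, which group the 20% describes, and whether Part II subjects count toward the subgroup 10 and 29. Add a small table of split-path power, overall and given a Part II pass, over a stated range of prevalence and negative-group rates. Leave alpha 0.05 as the per-group ceiling.
2. Reconcile 3.7 and 15.3.3. Where subgroups are defined, report CLEVER-1 positives as the group for objective 3.7, and report any continued negative subgroup separately under the same rule, since 15.7 lets it expand to 29. Otherwise use all evaluable subjects in the cohort.
3. Reconcile 15.4 with 15.3.2 and 15.3.3 so that Parts II and III use the 90% interval, which matches the one-sided 0.05.
4. Where accrual ends at the fourth benefit, report beside the plain proportion a CBR estimate and 90% interval that respect the two-stage and stopping rule, for example median-unbiased. Place this in 15.3.3 or the Part III SAP.

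The cost is wording, one small table and a few lines of code, with no extra subjects and no change to accrual. The stated power for the split path may look less favourable than 0.80.
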